## 6.5. WINDOWING CONVENTIONS

No visit windowing will be performed for this study.

## 6.6. STATISTICAL TESTS

The default significance level will be (5%); confidence intervals will be 95% and all tests will be two-sided, unless otherwise specified in the description of the analyses. In general, continuous variables will be summarized using number and percentage of participants, number and percentage of participants with missing values, mean, standard deviation, median, 25th-75th percentile (Q1-Q3), minimum and maximum. If there are no missing values the number of participants with missing values will be set to 0.

Categorical variables will be summarized using number of participants and percentages. Unless otherwise stated percentages are calculated based on the number of participants in the analysis set of interest and counts of missing observations will be included in the denominator. Counts of missing observations will be included as a separate category in table summaries. For by-visit summaries, denominators will include the number of participants in the analysis set of interest that are still present in the study at that visit.

## 6.7. COMMON CALCULATIONS

For quantitative measurements, change from baseline will be calculated as:

- Change from baseline = timepoint value – baseline value
- Percent Change from baseline =  $100 * (\text{timepoint value} - \text{baseline value}) / \text{baseline value}$ .

Change from baseline will only be calculated when both the timepoint and baseline values are non-missing.

Document: [\\quintiles.net\Enterprise\Apps\sasdata\SAS\sas\GSK\GSK4045154\PZAA7715\Biostatistics\Documentation\SAP\GSK\\_213152\\_PZAA7715\\_SAP\\_Final\\_v1.0\\_07SEP2022](\\quintiles.net\Enterprise\Apps\sasdata\SAS\sas\GSK\GSK4045154\PZAA7715\Biostatistics\Documentation\SAP\GSK_213152_PZAA7715_SAP_Final_v1.0_07SEP2022)

Author: PPD Version Number: 1.0

Version Date: 07SEP2022

Template No.: CS\_TP\_BS016 Revision 6

Reference: CS\_WI\_BS005

Effective Date: 02Dec2019

## 6.8. SOFTWARE VERSION

All analyses will be conducted using SAS version 9.4 or higher.

## 7. STATISTICAL CONSIDERATIONS

### 7.1. ADJUSTMENTS FOR COVARIATES AND FACTORS TO BE INCLUDED IN ANALYSES

There will be no adjustment for covariates in the analysis. In addition, as the study is open-label and only includes one arm, no adjustments will be made for randomization or blinding purposes.

### 7.2. MULTICENTER STUDIES

This study will be conducted by multiple investigators at multiple centers internationally.

When specified, statistical analysis will be presented by geographic region. Geographic region will be categorized as follows:

Geographic Region	Country
North America	United States, Canada
Europe	UK, Spain, Netherlands, France

### 7.3. MISSING DATA

Unless otherwise stated, missing data will not be imputed. Missing statistics should be presented as “nd” for “not determined” in tables.

Missing dates (incomplete or partial dates and handling of age calculations, disease history,

Document: [\\quintiles.net\Enterprise\Apps\sasdata\SAS\sas\GSK\GSK4045154\PZAA7715\Biostatistics\Documentation\SAP\GSK\\_213152\\_PZAA7715\\_SAP\\_Final\\_v1.0\\_07SEP2022](\\quintiles.net\Enterprise\Apps\sasdata\SAS\sas\GSK\GSK4045154\PZAA7715\Biostatistics\Documentation\SAP\GSK_213152_PZAA7715_SAP_Final_v1.0_07SEP2022)

Author: PPD Version Number: 1.0

Version Date: 07SEP2022

Template No.: CS\_TP\_BS016 Revision 6 Reference: CS\_WI\_BS005

Effective Date: 02Dec2019

AEs, prior and concomitant medications, subsequent anti-cancer therapy and death date) will be handled as per Appendix 2 of this SAP.

Missing efficacy data will be handled as described in Section 13.1.2 and 13.2.3 of this SAP.

## 7.4. MULTIPLE COMPARISONS/ MULTIPLICITY

As there is only one primary efficacy endpoint, no adjustments will be made for multiple comparisons.

## 7.5. EXAMINATION OF SUBGROUPS

There will be no subgroup analyses conducted for this study.

## 8. OUTPUT PRESENTATIONS

Appendix 1 shows conventions for presentation of data in outputs.

The templates provided with this SAP describe the presentations for this study and therefore the format and content of the summary tables CCI [REDACTED] and listings to be provided by IQVIA Biostatistics.

## 9. DISPOSITION AND WITHDRAWALS

All participants who provide informed consent will be accounted for in this study.

### 9.1. DISPOSITION

Participant disposition and withdrawals (including those due to COVID-19), and reasons for exclusion from each analysis set, including inclusion and exclusion criteria will be presented for the SCR set.

The following information will be reported:

Document: [\\quintiles.net\\Enterprise\\Apps\\sasdata\\SAs\\sas\\GSK\\GSK4045154\\PZAA7715\\Biostatistics\\Documentation\\SAP\\GSK\\_213152\\_PZAA7715\\_SAP\\_Final\\_v1.0\\_07SEP2022](\\quintiles.net\\Enterprise\\Apps\\sasdata\\SAs\\sas\\GSK\\GSK4045154\\PZAA7715\\Biostatistics\\Documentation\\SAP\\GSK_213152_PZAA7715_SAP_Final_v1.0_07SEP2022)

Author: PPD [REDACTED] Version Number: 1.0

Version Date: 07SEP2022

Template No.: CS\_TP\_BS016 Revision 6 Reference: CS\_WI\_BS005

Effective Date: 02Dec2019

- Total number of participants screened (i.e. participants who gave informed consent)
- Number of participants who discontinued from the study prior to study treatment overall and grouped by the main reason (e.g. the failed specific inclusion or exclusion criteria, adverse event, lost to follow-up, protocol non-compliance, death, progressive disease, withdrawal by participant and other)
- Number of re-screened participants
- Number of participants who received at least one dose of study treatment (SAF)
- Number of participants with treatment ongoing at the data cut-off date
- Number of participants off study treatment, grouped by main reason (treatment completed as per protocol, adverse event, lost to follow-up, protocol non-compliance, death, progressive disease, withdrawal by participant and other)
- Number of participants ongoing on the study at the data cut-off date
- Number of participants who completed/discontinued the study participation, with the associated main primary reason (study completed according to protocol, adverse event, lost to follow-up, protocol non-compliance, death, progressive disease, withdrawal by participant and other).

No percentages will be provided for the number of participants screened and re-screened including for the reasons participants discontinued from the study prior to study treatment. All other counts will include percentages based on the number of participants in the SAF.

A participant will be considered to have completed the study if the participant dies or otherwise progresses during the treatment or follow-up period or has been in follow-up for a maximum of 3 years or if they are in follow-up when the DCO date is reached, whichever is sooner.

The number of participants in each analysis set will be summarized overall.

A listing of participant disposition will include participant identifier, date of informed consent, included in the study, first/last study treatment date, date and reason for discontinuation of treatment, date and reason for discontinuation of the study, population flags, rescreened participant ID, date of screen failure and reason for screen failure. When the reason such as reason for discontinuation of treatment will be categorized as “Other, specify” or “Withdrawal by subject, specify”, the verbatim text as entered in the eCRF will be

Document: [\\quintiles.net\Enterprise\Apps\sasdata\SAStas\GSK\GSK4045154\PZAA7715\Biostatistics\Documentation\SAP\GSK\\_213152\\_PZAA7715\\_SAP\\_Final\\_v1.0\\_07SEP2022](\\quintiles.net\Enterprise\Apps\sasdata\SAStas\GSK\GSK4045154\PZAA7715\Biostatistics\Documentation\SAP\GSK_213152_PZAA7715_SAP_Final_v1.0_07SEP2022)

Author: PPD Version Number: 1.0

Version Date: 07SEP2022

Template No.: CS\_TP\_BS016 Revision 6

Reference: CS\_WI\_BS005

Effective Date: 02Dec2019

included in the listing. Participants who are re-screened will only be included once, with the details of participant identifier, date of screen failure and screen failure reason.

## 9.2. PROTOCOL DEVIATIONS

Details of the process for protocol deviation collection, review and finalization and definition of important protocol deviations will be presented in the Protocol Deviations Management Plan.

All protocol deviations classified as important will be listed including those due to COVID-19, if applicable, for the SAF. The listing will include: participant identifier, category of the deviation (e.g. inclusion/exclusion criteria), and a description of the deviation.

## 10. DEMOGRAPHIC AND OTHER BASELINE CHARACTERISTICS

Demographic data and other baseline characteristics will be presented for the SAF.

No statistical testing will be carried out for demographic or other baseline characteristics.

### 10.1. DEMOGRAPHICS

The following demographic characteristics will be summarized for this study:

- Age (years) - calculated relative to date of consent
- Age Categories:
  - < 65 years, ≥ 65 years
  - 65-74 years, 75-84 years, ≥ 85 years.
- Sex (male, female)
- Race
  - For participants reporting one race only: White, Black or African American, Asian, American Indian or Alaska Native, Native Hawaiian or other Pacific Islander, Not collected at the site, Other.
  - For participants reporting several races, all combinations will be reported under

Document: [\\quintiles.net\Enterprise\Apps\asdata\SAS\asas\GSK\GSK4045154\PZAA7715\Biostatistics\Documentation\SAP\GSK\\_213152\\_PZAA7715\\_SAP\\_Final\\_v1.0\\_07SEP2022](\\quintiles.net\Enterprise\Apps\asdata\SAS\asas\GSK\GSK4045154\PZAA7715\Biostatistics\Documentation\SAP\GSK_213152_PZAA7715_SAP_Final_v1.0_07SEP2022)

Author: PPD Version Number: 1.0

Version Date: 07SEP2022

Template No.: CS\_TP\_BS016 Revision 6

Reference: CS\_WI\_BS005

Effective Date: 02Dec2019

‘More than one race’ category.

- Ethnicity (Hispanic or Latino, not Hispanic or Latino)
- Geographic Region (Europe, North America)

Details of alcohol usage and nicotine consumption from the “Alcohol Consumption” and “Nicotine Usage” eCRF forms will be collected at baseline and will be included in a listing of Demographic characteristics including sex, race (all reported races in the case of multiple races and details in the case of “other” race), ethnicity, geographic region, age (years), age category, height, weight and BMI will be presented in a listing. The listing will also include positive history of Tuberculosis (TB) exposure, TB collection date, assay and result.

## 10.2. DERIVATIONS

- Age (years) = (date of given informed consent – date of birth +1) / 365.25
- Geographic Region will be determined from investigator site codes
- BMI (kg/ m^2) = weight (kg)/ height (m).

## 11. MEDICATIONS

Medications will be coded using the World Health Organization Drug Dictionary (WHO-DD), B3.

See Appendix 2 for handling of partial dates for medications.

## 11.1. PREVIOUS ANTI-CANCER TREATMENTS AND PROCEDURES

Prior Anti-cancer Therapies will be captured on the “Prior Anti-cancer Drug Therapies” eCRF page and the following will be summarized:

- Participants with at least one previous anti-cancer drug therapy
- Number of any previous anticancer therapy regimens: 0, 1, 2, >2. Also mean, SD, median, Q1, Q3, min and max
- Intent of therapy (including all treatment regimens): Neoadjuvant / Adjuvant / Metastatic or Locally advanced

Document: [\\quintiles.net\Enterprise\Apps\sasdata\SAStas\GSK\GSK4045154\PZAA7715\Biostatistics\Documentation\SAP\GSK\\_213152\\_PZAA7715\\_SAP\\_Final\\_v1.0\\_07SEP2022](\\quintiles.net\Enterprise\Apps\sasdata\SAStas\GSK\GSK4045154\PZAA7715\Biostatistics\Documentation\SAP\GSK_213152_PZAA7715_SAP_Final_v1.0_07SEP2022)

Author: PPD Version Number: 1.0

Version Date: 07SEP2022

Template No.: CS\_TP\_BS016 Revision 6 Reference: CS\_WI\_BS005

Effective Date: 02Dec2019

- Best response of last treatment regimen: Complete Response (CR) / Partial Response (PR) / Stable Disease (SD) / Progressive Disease (PD) / Non-Complete Response/Non-Progressive Disease (non-CR/non-PD) / Not Assessable / Unknown / Not applicable
- The time since completion of first-line (1L) of platinum-based treatment will also be summarized. Platinum-based treatment will be identified for participants who received at least one platinum-based drug (cisplatin, oxaliplatin or carboplatin). The time since completion will be measured using the maximum stop date within the identified regimen (maximum start date will be used in case the stop date is not available).
- Number of participants per 1L regimen, e.g., cisplatin/gemcitabine.

If there is a platinum-based treatment with an intent of metastatic/locally advanced, then the first of these will be considered as first-line. Otherwise, the first platinum-based treatment (with intent of adjuvant or neoadjuvant) will be considered first-line.

A listing of previous anti-cancer drugs will include participant identifier, age, sex, race, regimen name, medication(s), start date, end date, intent of therapy, Line Number for Metastatic/Locally Advanced, best response, date of progression and whether Radiotherapy was administered as part of the therapy.

## 11.2. PREMEDICATIONS FOR BINTRAFUSP ALFA

Premedications are medications administered per protocol on the same day as, but prior to, the study treatment to minimize potential infusion-related reactions.

Premedications will be included in a listing of infusion-related reactions.

## 12. STUDY TREATMENT EXPOSURE

Exposure to study treatment in weeks will be presented for the SAF.

The date of first study treatment administration will be taken from the eCRF “Bintrafusp Alfa Administration Details” form. The date of last study treatment will be taken from the eCRF “Bintrafusp Alfa Termination” form.

For the analysis of exposure, a dose is regarded to be administered if the actual dose received is > 0mg.

Document: [\\quintiles.net\Enterprise\Apps\sasdata\SAS\sas\GSK\GSK4045154\PZAA7715\Biostatistics\Documentation\SAP\GSK\\_213152\\_PZAA7715\\_SAP\\_Final\\_v1.0\\_07SEP2022](\\quintiles.net\Enterprise\Apps\sasdata\SAS\sas\GSK\GSK4045154\PZAA7715\Biostatistics\Documentation\SAP\GSK_213152_PZAA7715_SAP_Final_v1.0_07SEP2022)

Author: PPD Version Number: 1.0

Version Date: 07SEP2022

Template No.: CS\_TP\_BS016 Revision 6

Reference: CS\_WI\_BS005

Effective Date: 02Dec2019

Interruptions, compliance, and dose changes are not taken into account for duration of exposure.

Summaries of exposure will include:

- Duration of treatment (weeks)
- Total number of infusions received
- Cumulative dose (mg)
- Dose intensity (mg/cycle)
- Relative dose intensity (%) as a continuous variable, and categorized as
  - < 80%
  - 80%-90%
  - > 90%.

Study treatment exposure will be included in a listing of study treatment which will include participant identifier, age, sex, race, visit, infusion start date and time, infusion end date and time, infusion rate (mL/hr), actual dose (mg), route, administration modification including dose not given and reason for modification.

## 12.1. DERIVATIONS

Duration of treatment (weeks) = (date of last dose – date of first dose + 14)/7.

Total number of 2-week cycles is defined as the duration of therapy (weeks) /2.

Cumulative dose (mg) per participant is the sum of the total study treatment that the participant received (actual dose) over the duration of exposure (i.e. total study treatment administered (mg)).

Dose intensity of treatment (mg/cycle) per 2-week cycle is defined as cumulative dose of treatment divided by (duration of treatment (in weeks)/2)

Relative dose intensity is defined as the actual dose intensity divided by the planned dose

Document: [\\quintiles.net\Enterprise\Apps\sasdata\SAS\sas\GSK\GSK4045154\PZAA7715\Biostatistics\Documentation\SAP\GSK\\_213152\\_PZAA7715\\_SAP\\_Final\\_v1.0\\_07SEP2022](\\quintiles.net\Enterprise\Apps\sasdata\SAS\sas\GSK\GSK4045154\PZAA7715\Biostatistics\Documentation\SAP\GSK_213152_PZAA7715_SAP_Final_v1.0_07SEP2022)

Author: PPD Version Number: 1.0  
Version Date: 07SEP2022

Template No.: CS\_TP\_BS016 Revision 6 Reference: CS\_WI\_BS005

Effective Date: 02Dec2019

intensity per cycle and expressed in a percentage.

## 13. EFFICACY AND EXPLORATORY OUTCOMES

### 13.1. PRIMARY EFFICACY

The primary efficacy analysis will be performed on the SAF. Details of tumor assessment based on imaging will be listed and will include: participant ID, age, sex, race, first and last bintrafusp alfa administration date, confirmed best overall response, date for first subsequent anti-cancer therapy, date of death, visit, date of imaging(day), Lesion type, Sum of Lesion Diameters (mm), Change from baseline (%) and overall response. The listing also includes lesion ID, size, status, site, type, method and response for each lesion type, as applicable.

#### 13.1.1. PRIMARY EFFICACY VARIABLE(S) & DERIVATION(S)

The primary efficacy endpoint is the confirmed objective response by the investigator. Overall response rate (ORR) is defined as the percentage (%) of participants with a best overall response (BOR) of PR or CR as assessed by the investigator using RECIST 1.1 out of the total number of participants in the SAF. Tumor response i.e., complete response (CR), partial response (PR), and stable disease (SD), and progressive disease (PD) will be based on the assessments from the investigators' assessment of objective evidence (e.g., radiological scan). Overall responses will be measured in accordance with the RECIST v1.1 (Eisenhauer EA, 2009).

Lesion assessment method and timing, evaluation of disease, disease progression and response criteria will be conducted according to RECIST (version 1.1) as outlined in Section 8.3 of the protocol. If there are multiple scan dates associated with an evaluation, the earliest of the scan dates associated with the evaluation will be used as the date of assessment.

Best overall response (BOR) will be assessed based on the tumor response determined by the investigator at each evaluation timepoint from the first study treatment until the first documented disease progression for RECIST criteria. Only tumor assessments performed before the start of any further anticancer treatment will be considered in the assessment of

Document: [\\quintiles.net\Enterprise\Apps\sasdata\SAS\sas\GSK\GSK4045154\PZAA7715\Biostatistics\Documentation\SAP\GSK\\_213152\\_PZAA7715\\_SAP\\_Final\\_v1.0\\_07SEP2022](\\quintiles.net\Enterprise\Apps\sasdata\SAS\sas\GSK\GSK4045154\PZAA7715\Biostatistics\Documentation\SAP\GSK_213152_PZAA7715_SAP_Final_v1.0_07SEP2022)

Author: PPD Version Number: 1.0

Version Date: 07SEP2022

Template No.: CS\_TP\_BS016 Revision 6

Reference: CS\_WI\_BS005

Effective Date: 02Dec2019

BOR. Clinical deterioration will not be considered as documented disease progression.

Confirmed BOR according to RECIST 1.1 (Eisenhauer EA, 2009) will be assessed according to the following rules:

- CR = at least two determinations of CR at least 4 weeks apart and before progression.
  - Note: It is reasonable to consider CR-NE-CR or CR-PR-CR as CR as long as the second CR is more than 28 days away from the first timepoint.
- PR = at least two determinations of PR at least 4 weeks apart and before progression (and not qualifying for a CR)
  - Note: It is reasonable to consider PR-NE-PR or PR-SD-PR as PR as long as the second PR is more than 28 days away from the first timepoint.
- SD = at least one SD assessment (or better)  $\geq$  6 weeks after first date of study treatment and before progression (and not qualifying for CR or PR)
- PD = progression  $\leq$  16 weeks after first date of study treatment (and not qualifying for CR, PR or SD)
- NE = all assessments are NE or participant has a missing (or not evaluable) baseline tumor assessment and/or no (or not evaluable) tumor assessments on-treatment, or participant does not complete any of the following response above.

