Bintrafusp alfa administration		X	X	X	X	X	X	X	Q2W				Bintrafusp alfa is administered as a 1200 mg IV infusion over 1 hour (-10 minutes/+20 minutes; ie, over 50 to 80 minutes) Q2W for up to 2 years (or up to 2 years from confirmed CR). See Section 6.1 for information.	

	Screening	Intervention (treatment) Period								Safety Follow-up		Long Term Follow-up	Notes	
Assessment and Procedures	45 Day- to first dose	V1	V2	V3	V4	V5	V6	V7	Until PD	EOT	28 Days (±5 Days) After Last Treatment	12 Weeks (± 2 Weeks) After Last Treatment	Every 12 Weeks (± 2 Weeks)	D1: All assessments must be performed on day indicated (unless noted in assessment "Notes"). Day 15 through PD: Visits can be performed ±3 days. EOT: On day of or within 7 days of decision to discontinue. Follow up: Visits can be performed ±2 Weeks.
		W1	W3	W5	W7	W9	W11	W13						
		D1	D15	D29	D43	D57	D71	D85						
Response Assessments														
Tumor evaluation/staging (CT Scan/MRI/ other established methods)	X					X			Q8W up to 6 months., then Q12W	X	X		CT scan with contrast of the chest, abdomen, and pelvis is required. Screening scans for lesion assessments are required within 28 days of first dose. See Section 8.3 for additional information Q8W for the first 6 months (mos.) and Q12W thereafter, and at the final study visit. Schedule should not be affected by dose interruptions/delays. Confirmation of CR and/or PR should be performed at the next scheduled assessment but no sooner than 4 weeks. Before stopping the treatment, progressive disease should be confirmed by imaging at least 4 weeks after progression. See Section 7.1.1. If discontinued intervention without documented progression, then continue imaging Q8W for the first 6 months followed by Q12W until documented PD, or the start of any new anti-cancer therapy. A bone scan should be done as clinically indicated at screening and beyond. TA brain CT/MRI scan should be performed as clinically indicated	

	Screening	Intervention (treatment) Period								Safety Follow-up		Long Term Follow-up	Notes				
Assessment and Procedures	45 Day- to first dose	V1	V2	V3	V4	V5	V6	V7	Until PD	EOT	28 Days (\pm 5 Days) After Last Treatment	12 Weeks (\pm 2 Weeks) After Last Treatment	Every 12 Weeks (\pm 2 Weeks)	D1: All assessments must be performed on day indicated (unless noted in assessment "Notes"). Day 15 through PD: Visits can be performed \pm 3 days. EOT: On day of or within 7 days of decision to discontinue. Follow up: Visits can be performed \pm 2 Weeks.			

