### 13.1.3. FINAL ANALYSIS OF PRIMARY EFFICACY VARIABLE(S)

Confirmed BOR will be summarized as the number and percentage of participants with confirmed CR, PR, SD, PD or NE. In addition, the number of participants achieving objective response will be summarized. The corresponding two-sided 95% Confidence Interval (CI) for ORR will be calculated using the Clopper-Pearson (exact) method (Clopper C, 1934) with exact CI for binomial proportion as computed by default by the FREQ procedure using the EXACT option. There will be no adjustments for multiplicity.

Document: [\\quintiles.net\Enterprise\Apps\sasdata\SAS\sas\GSK\GSK4045154\PZAA7715\Biostatistics\Documentation\SAP\GSK\\_213152\\_PZAA7715\\_SAP\\_Final\\_v1.0\\_07SEP2022](\\quintiles.net\Enterprise\Apps\sasdata\SAS\sas\GSK\GSK4045154\PZAA7715\Biostatistics\Documentation\SAP\GSK_213152_PZAA7715_SAP_Final_v1.0_07SEP2022)

Author: PPD Version Number: 1.0

Version Date: 07SEP2022

Template No.: CS\_TP\_BS016 Revision 6

Reference: CS\_WI\_BS005

Effective Date: 02Dec2019

- The following reasons for non-evaluable confirmed best overall response will also be included in the summary:
  - No baseline assessment (if applicable)
  - No post-baseline assessments due to death within 8 weeks after the start of study treatment
  - No post-baseline assessments due to other reasons
  - All post-baseline assessments have overall response “Non-evaluable”
  - New anticancer therapy started before first evaluable post-baseline assessment
  - SD of insufficient duration (<6 weeks after the start of study treatment)
  - No evaluable tumor assessment >16 weeks followed by PD (i.e. tumor assessment of PD was >16 weeks after start of study treatment and there was no evaluable tumor assessment in between)
  - Not determined category may also be added if applicable.

CCI

Document: [\\quintiles.net\Enterprise\Apps\sasdata\SA\SAsas\GSK\GSK4045154\PZAA7715\Biostatistics\Documentation\SAP\GSK\\_213152\\_PZAA7715\\_SAP\\_Final\\_v1.0\\_07SEP2022](\\quintiles.net\Enterprise\Apps\sasdata\SA\SAsas\GSK\GSK4045154\PZAA7715\Biostatistics\Documentation\SAP\GSK_213152_PZAA7715_SAP_Final_v1.0_07SEP2022)

Author: PPD Version Number: 1.0

Version Date: 07SEP2022

Template No.: CS\_TP\_BS016 Revision 6 Reference: CS\_WI\_BS005

Effective Date: 02Dec2019

CCI

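### Read as written, SAP 13.1.1 scores a single PR followed by a single CR as SD, so that participant is a non-responder in the primary confirmed ORR

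*SAP*

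**What the plan says.** SAP 13.1.1 makes confirmed objective response by investigator the primary endpoint. ORR is the percentage of the Safety/Treated set whose best overall response (BOR) is CR or PR. Confirmed BOR "will be assessed according to the following rules", and the rules are these:

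- CR needs two CRs at least 4 weeks apart before progression. A note adds "It is reasonable to consider CR-NE-CR or CR-PR-CR as CR", provided the second CR is more than 28 days from the first timepoint.
- The PR rule reads "PR = at least two determinations of PR at least 4 weeks apart and before progression (and not qualifying for a CR"). Its note adds "It is reasonable to consider PR-NE-PR or PR-SD-PR as PR", and puts a timing condition on these sequences that differs from the rule: "as long as the second PR is more than 28 days away from the first timepoint".
- The SD rule opens with "SD = at least one SD assessment (or better"). It looks for such a scan at 6 weeks or later, ahead of any progression, when neither response rule is met.

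SAP 13.1.3 then reports the result: "Confirmed BOR will be summarized as the number and percentage of participants with confirmed CR, PR, SD, PD or NE". The ORR carries an exact 95% interval.

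The protocol deals with the timing of confirmation. Table 1 says "Confirmation of CR and/or PR should be performed at the next scheduled assessment but no sooner than 4 weeks", and Section 8.3.1.1 asks for a confirmatory assessment at least 4 weeks after a CR or PR. Neither says which category confirms a PR.

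**The concern.** Each response rule asks for the same category twice, and every sequence named in the notes starts and ends in the same category. The wording that admits a better result appears only in the SD rule. A response that deepens from PR to CR, with each seen once, therefore has no rule that makes it a response, while one that lapses from PR to SD and returns to PR does.

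The pattern can arise under this design. BOR stops at first progression and ignores scans after new anticancer therapy. No data enter the database after the cut-off. Scans move from every 8 to every 12 weeks after 6 months, so a recent CR may have no repeat scan by then.

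At stake is the numerator of the primary endpoint. For this pattern the literal rule can only lower it. Two programmers could also reach different ORRs, one coding the listed rules and the other coding what they take the RECIST citation to intend.

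**Working it through.** The plan has no figure of its own to reproduce: n = 25 (Protocol 9.2) is stated without a visible calculation.

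**Step 1: apply the rules as written.** Inputs are the SAP 13.1.1 rules, truncated at first PD, with 4 weeks = 28 days and 6 weeks = 42 days. Scan times are counted from first dose.

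| Sequence (day) | As written | If a later PR or CR confirms a PR |
|---|---|---|
| PR 56, CR 112, PD 168 | SD | PR |
| PR 56, CR 112, no later scan | SD | PR |
| SD 56, PR 112, CR 168, PD 252 | SD | PR |
| PR 53, CR 109 (scan window used) | SD | PR |
| PR 10, CR 40 (unscheduled, both before day 42) | NE | PR |
| PR 56, PR 112, CR 168, PD 252 | PR | PR |
| PR 56, CR 112, CR 168 | CR | CR |

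The route is the same in the SD rows: one CR fails the CR rule, one PR fails the PR rule, and a scan at 6 weeks or later then satisfies SD. The first scheduled scan is at 8 weeks with a 3-day window, so 56 − 3 = 53 days at the earliest, which is past 42. The NE outcome therefore needs off-schedule scans.

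**Step 2: how narrow the gap is.** Take all 4 × 4 × 4 = 64 sequences of three scheduled scans from {CR, PR, SD, NE}, followed by PD.

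- As written: at least two CRs, 3 × 3 + 1 = 10; at least two PRs, another 10; total 20 responses.
- One PR before one CR, with the third scan SD or NE: 3 positions × 2 = 6 (PR-CR-SD, PR-CR-NE, PR-NE-CR, SD-PR-CR, NE-PR-CR, PR-SD-CR). Counting all six gives 26; leaving out PR-SD-CR gives 25.
- One CR before one PR: 6 more, giving 32 if order were ignored.

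These are counts of patterns, not probabilities.

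**Step 3: effect on ORR.** One participant is 1/25 = 4.0 percentage points. Clopper-Pearson limits are Beta(0.025; x, n − x + 1) and Beta(0.975; x + 1, n − x). The responder counts are illustrative.

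- x = 5: 20.0% (6.8 to 40.7), width 33.9 points
- x = 4: 16.0% (4.5 to 36.1), width 31.6 points

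**Step 4: the interval wording.** The CR and PR rules say at least 4 weeks; their notes say more than 28 days. PR on day 56, NE on day 70 and PR on day 84 are 84 − 56 = 28 days apart, so the rule gives PR and the note gives SD. Scheduled 8-weekly scans are never closer than 56 − 6 = 50 days, so this touches only extra scans. Protocol 8.3.1.1 allows those. SAP 6.4, partly redacted, keeps post-baseline unscheduled visits out of table summaries, so whether extra scans enter BOR is itself unclear.

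**The case against.** The best reply is that the rules sit under a RECIST 1.1 heading, the same section says responses are measured by RECIST 1.1, and the protocol speaks of confirming a response, CR or PR alike. The notes call their sequences reasonable, which can be read as giving examples. On that view a competent programmer would let the CR confirm the PR, and the SAP has only left a phrase out. Further detail may sit in the study reference manual or the output templates, which are not available here.

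Part of this stands. The text does not show that the sponsor chose to exclude such participants; an omission is at least as likely. But the SAP states explicit rules and says they will be applied, and no visible passage supplies a different one. The possibility of two readings is itself a reason to settle the wording.

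It is also fair to say that the effect may be nil, that one case moves ORR by 4 points inside an interval more than 30 points wide, and that the listing in SAP 13.1 shows each overall response beside confirmed BOR, so a reader could find the case. These points limit the weight of the concern and do not remove it.

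A reader might infer that every PR deepening to CR is lost. It is not: PR-PR-CR and PR-CR-PR score PR, and PR-CR-CR scores CR. A reader might also express one case as a share of expected responders, using the 14% to 21% response rates in Protocol 2.2.1. Those rates belong to other drugs, and at n = 25 they give 3.5 to 5.25 responders, which are not possible counts.

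**Conclusion.** The concern holds as a defect in the written derivation. A single PR followed at least 4 weeks later by a single CR is SD under SAP 13.1.1, or NE if no assessment is at 6 weeks or later, and a non-response either way. Each case costs 4 points of ORR. This rests on reading the rules literally and on the ORR denominator being 25.

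A reader might infer that the primary result is materially biased or that a go/no-go decision could turn on this. The documents do not support that: they give no count of affected participants, and no decision threshold is visible (parts of Protocol 9.1 and 9.4.2 are redacted). It should be fixed because it concerns the primary endpoint and the repair is cheap. The interval mismatch is secondary and minor.

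**What to change.** Before database lock:

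1. Reword the PR rule: *PR = a determination of PR followed by a determination of PR or better (PR or CR) at least 4 weeks later, both before progression, where the CR rule is not met.* Keep the order explicit; two results of PR or better in any order would also admit CR followed by PR.
2. Add PR-NE-CR to the PR note.
3. Record the change in the SAP and report how many participants it reclassifies. The study is open-label and the change can only raise ORR, so the reader should see its effect.
4. State whether PR-SD-CR, and a single CR followed by a single PR, count as response. Both are the sponsor's choice; the second is SD as written and stays SD under step 1.
5. Minor: if the interval is aligned, use at least 4 weeks (28 days) in both the CR and PR notes, and say, consistently with SAP 6.4, whether unscheduled scans enter BOR.

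The cost is a few reworded lines and one condition in the BOR program. No new data are needed.
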